6.6.1.1 Adverse Events of Special Interest

Please see [Appendix A](#) for the full list of AESIs.

6.6.2 Serious Adverse Events

A SAE is defined as any untoward medical occurrence that at any dose results in one or more of the following:

- Death.
- Is life-threatening (i.e., the subject was, in the opinion of the investigator, at immediate risk of death from the event as it occurred); it does not refer to an event which hypothetically might have caused death if it were more severe.
- Required or prolonged hospitalization.
- Persistent or significant disability/incapacity (i.e., the event causes a substantial disruption of a person’s ability to conduct normal life functions).
- Congenital anomaly/or birth defect.
- An important and significant medical event that may not be immediately life threatening or resulting in death or hospitalization but, based upon appropriate medical judgment, may jeopardize the subject or may require intervention to prevent one of the other outcomes listed above.

AEs which do not fall into these categories are defined as **non-serious**.

It should be noted that a severe AE need not be serious in nature and that a SAE need not, by definition, be severe.

SAEs will be captured both on the VSAE form as well as on the AE eCRF. All SAEs will be evaluated by the investigator for relationship of the event to study vaccine. SAEs that are judged to be possibly or probably related to the study vaccine should be reported to the Sponsor as related (i.e., suspected) events.

The relationship of the study treatment to an SAE will be determined by the investigator based on the following definitions:

1. Related/suspected

The SAE is judged by the investigator to be possibly or probably related to the study vaccine on the AE CRF page (see [section 6.6.1](#)).

2. Not Related

The SAE is not related if exposure to the study vaccine has not occurred, **or** the occurrence of the SAE is not reasonably related in time, **or** the SAE is considered unlikely to be related to use of the study vaccine, i.e., there are no facts (evidence) or arguments to suggest a causal relationship.

In addition, SAEs will be evaluated by the Sponsor or designee for “expectedness.” An unexpected AE is one that is not listed in the current Summary of Product Characteristics or the Investigator’s Brochure or an event that is by nature more specific or more severe than a listed event.

In addition, a pre-existing event or condition that results in hospitalization should be recorded on the Medical History eCRF. If the onset of an event occurred before the subject entered the study (e.g., any pre-planned hospitalization for conditions like cosmetic treatments or for non-emergency routine visits for a pre-existing condition), the hospitalization would not lead to an AE being classified as serious unless, in the view of the investigator, hospitalization was prolonged as a result of participation in the clinical trial or was necessary due to a worsening of the pre-existing condition.

6.6.3 Methods for Assessing and Recording AEs and SAEs

The period of observation for AEs extends from the time the subject signs informed consent until he or she completes the specified safety follow-up period, approximately 13 months after the first vaccination or terminates the study early (whichever comes first).

AEs occurring after the ICF is signed but prior to receiving study vaccine/product will be documented as an AE and recorded on the AEs eCRF and within source documents. However, AEs occurring prior to receipt of any study vaccine will be analyzed separately from “treatment emergent” AEs (AEs occurring after administration of the first study vaccine).

All AEs meeting criteria for reporting, regardless of severity, will be monitored by the investigator until resolution or stabilization. All subjects experiencing AEs - whether considered associated with the use of the study vaccine or not - must be monitored until symptoms subside and any abnormal laboratory values have returned to baseline, or until there is a satisfactory explanation for the changes observed, or until death, in which case a full pathologist’s report should be supplied, if possible. All findings must be reported on an AEs eCRF and on the VSAE form, if necessary, which is part of the Investigator Site File. All findings in subjects experiencing AEs must be reported also in the subject's medical records.

All SAEs which occur during the course of the study, whether considered to be associated with the study vaccination or not, must be reported **within 24 hours of the site becoming aware of the event** by telephone or fax to the Sponsor. Contact details for submitting SAEs to the Sponsor or its designee and instructions for completion of documentation will be provided in a handout located in the Investigator Site File.

All SAEs are also to be documented on the AE eCRF. Any medication or other therapeutic measures used to treat the AE will be recorded on the appropriate eCRF(s) in addition to the outcome of the AE.

After receipt of the initial report, representatives of the Sponsor will contact the investigator if it is necessary to obtain further information for assessment of the event.

All SAEs must be reported by the investigator to his/her corresponding EC or IRB and applicable regulatory authorities in accordance with institutional policy/regulatory requirements and adequate documentation of this notification must be provided to the Sponsor.

The Sponsor or its designee must also comply with the applicable regulatory requirement(s) related to the reporting of unexpected serious and non-serious adverse vaccine reactions (also referred to as “SUSARs”) to the regulatory authority(ies) and the IRB/EC. If a SUSAR or other safety signal relating to use of one of the study vaccines is reported to the Sponsor or its designee, the Sponsor will communicate the information to the investigator and the investigator will be responsible for submitting this information to the EC or IRB and other relevant authorities.

Post-Study Events

Any suspected SAE that occurs outside of the protocol-specified follow-up period or after the end of the study but considered to be caused by the study vaccine must be reported to the Sponsor or its designee. Instructions and contact details for collecting and reporting these suspected SAEs will be provided to the investigator.

6.6.4 Pregnancies

To ensure subjects' safety, each pregnancy in a subject on study vaccine must be reported to the Sponsor within 24 hours of the site learning of its occurrence. If the subject agrees to submit this information, the pregnancy must be followed to determine outcome, including spontaneous or voluntary termination, details of the birth, and the presence or absence of any birth defects, congenital abnormalities, or maternal and/or newborn complications. This follow-up should occur even if intended duration of safety follow-up for the study has ended.

Pregnancy data must be recorded on a Pregnancy Report CRF (initial report) and Pregnancy Follow-Up CRF (outcome report) and reported to the Sponsor. Contact details for submitting the case report forms will be described in the Investigator Site File.

Any pregnancy outcome meeting the definition of a SAE (see [section 6.6.2](#)) must also be reported on the VSAE Report Form.

6.7 Safety Laboratory Measurements

This study has no safety laboratory measurements.

6.8 Other Measurements

This study has no other measurements.

6.9 Data Monitoring Committee

No Data Monitoring Committee is planned in this study.

7.0 ENDPOINTS AND STATISTICAL ANALYSES

7.1 Endpoints

7.1.1 Primary Immunogenicity Endpoints

The primary immunogenicity endpoints will be based on HI antibody response to the H5N1 vaccine strain for subjects ≥ 18 years of age, in the aH5N1c vaccine groups only.

- GMT at Day 43 by lot
- Percentage of subjects with HI titer $\geq 1:40$ on Day 43 by age cohort (18 to <65 years of age and ≥ 65 years of age) for the pooled lots.

7.1.2 Secondary Immunogenicity Endpoints

The secondary measures of immunogenicity, as determined by the HI assay, against the H5N1 homologous strain, include the following:

- GMT at Day 1, Day 22, Day 43, and Day 183 by vaccine group (aH5N1c or placebo) and by age cohort (18 to <65 years of age and ≥ 65 years of age).
- Percentage of subjects with HI titer $\geq 1:40$ on Day 1, Day 22, and Day 183 by vaccine group (aH5N1c or placebo) and by age cohort (18 to <65 years of age and ≥ 65 years of age).
- Percentage of subjects achieving seroconversion (defined as: HI titer $\geq 1:40$ for subjects negative at baseline [HI titer $< 1:10$]; or a minimum 4-fold increase in HI titer for subjects positive at baseline [HI titer $\geq 1:10$]) on Day 22, and Day 43 by vaccine group (aH5N1c or placebo) and by age cohort (18 to <65 years of age and ≥ 65 years of age).
- Geometric mean HI titer (GMT) at Day 1, Day 22, Day 43 and Day 183 by vaccine group (aH5N1c or placebo) and by age cohort (18 to <60 years of age and ≥ 60 years of age)
- Percentage of subjects with HI titer $\geq 1:40$ on Day 1, Day 22, Day 43, and Day 183 by vaccine group (aH5N1c or placebo) and by age cohort (18 to <60 years of age and ≥ 60 years of age)
- Percentage of subjects achieving seroconversion (defined as: HI titer $\geq 1:40$ for subjects negative at baseline [HI titer $< 1:10$]; or a minimum 4-fold increase in HI titer for subjects positive at baseline [HI titer $\geq 1:10$]) on Day 22, and Day 43 by vaccine

group (aH5N1c or placebo) and by age cohort (18 to <60 years of age and \geq 60 years of age)

- Geometric mean ratio (GMR) of HI titer: Day 22/Day 1, Day 43/Day 1 by vaccine group (aH5N1c or placebo) and by age cohort (18 to <60 years of age and \geq 60 years of age)

7.1.3 Secondary Efficacy Endpoints

Not applicable.

7.1.4 Safety Endpoints

The measures for assessing safety and tolerability are as follows:

- Percentages of subjects with solicited local, solicited systemic and other AEs as measured for 7 days (inclusive) following each (1st and 2nd) and any (1st or 2nd) vaccination, by vaccine group (and calculated for several time intervals after vaccination⁷: 30 minutes, 1 to 3 days (without 30 min), 4 to 7 days, and 1 to 7 days (without 30 min), and 1 to 3 days (including 30 minutes) and 1 to 7 days (including 30 minutes).
- Percentages of subjects with any unsolicited AEs reported through 21 days after each (1st and 2nd) and any (1st or 2nd) vaccination by vaccine group.
- Percentages of subjects reporting SAEs, AESIs, NOCD, AEs leading to vaccine/study withdrawal, and medically attended AEs, and concomitant medications associated with these events as collected from Day 1 to Day 387, by vaccine group.

7.1.5 Other Endpoints

Not applicable.

7.1.6 Exploratory Endpoints

Not applicable.

⁷ Timeframes shown relate to each vaccination; for second vaccination, please see Time and Events table for corresponding study visit days for each procedure

7.2 Success Criteria

7.2.1 Success Criteria for Co-Primary Objectives

Lot-to-lot consistency, derived from Day 43 HI titers for each aH5N1c lot, will be claimed if, for subjects ≥ 18 years of age in the Per Protocol Set, the two-sided 95% confidence intervals (CIs) of all the three pairwise comparisons (GMT(Group A)/ GMT(Group B), GMT(Group A)/ GMT(Group C), GMT(Group C)/ GMT(Group B)) fall within 0.667 and 1.5. Significance level to all these tests is $\alpha = 5\%$, which needs no adjustment for multiplicity as all hypotheses have to be rejected (intersection-union test problem).

Furthermore after lot-to-lot consistency is achieved, CBER criteria for the percentage of subjects with HI titer $\geq 1:40$ on Day 43 will be assessed as below, for subjects from both age cohorts (18 to 65 years of age and ≥ 65 years of age) on pooled lots. The overall power to fulfill those CBER criteria is 98%.

Immunogenicity according to CBER in subjects 18 - < 65 years of age

The aH5N1c vaccines immunogenicity will be evaluated in subjects 18 to < 65 years of age, using the following measurements according to the current CBER criteria for the adult population (CBER 2007):

- The lower bound of the adjusted two-sided 95% CI for the percentage of subjects achieving an HI antibody titer $\geq 1:40$ should meet or exceed 70%.

Immunogenicity according to CBER in subjects ≥ 65 years of age

The aH5N1c vaccine immunogenicity will be evaluated in subjects ≥ 65 years of age, using the following measurements according to the current CBER criteria for the ≥ 65 years of age population (CBER 2007):

- The lower bound of the adjusted two-sided 95% CI for the percentage of subjects achieving an HI antibody titer $\geq 1:40$ should meet or exceed 60%.

The study will be considered a success if both lot-to-lot consistency for subjects aged ≥ 18 years, and CBER criteria (titer above 1:40) for both age cohorts (18-65 years and ≥ 65 years) are met.

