Statistical Analysis of Primary Objectives: Co-Primary Immunogenicity Objectives: The lot-to-lot consistency will be claimed if the two-sided 95% confidence intervals (CIs) of all the three pairwise comparisons (GMT(Group A)/ GMT(Group B), GMT(Group A)/ GMT(Group C), GMT(Group C)/ GMT(Group B)) fall within 0.667 and 1.5. Significance level to all these tests is $\alpha = 5\%$, which needs no adjustment for multiplicity as all hypotheses have to be rejected (intersection-union test problem). With the proposed sample size, assuming a standard deviation of 0.85 for the log ₁₀ antibody titers (for each vaccine lot), approximate pairwise equivalence of factor 1 and independency, a single equivalence test based on 718 subjects per lot group has a power of 95%. The resulting overall power is approximately 86%, because the total number of comparisons is three. To account for dropouts (approximately 10%), a total of n=798 per lot should be recruited. After demonstrating success of the lot-to-lot consistency, the achievement of the CBER criteria (co-primary objective) will be claimed if the lower bound of the two-sided 95% CI for the percent of subjects achieving an HI antibody titer $\geq 1:40$ should meet or exceed 70% or 60% (for subjects 18 - <65 years of age and subjects ≥ 65 years of age, respectively) for all lots pooled. With the proposed sample size of 1077 per age cohort and the assumed proportions based on previous studies, such as V89_04 and V89_13 the power to meet or exceed 70% or 60% of the subjects achieving an HI antibody titer $\geq 1:40$ is 82% - > 99% (based on the age cohort). Primary Safety Objective: There is no statistical null hypothesis associated with the safety objective, which will be analyzed descriptively.		
Planned Analyses: An interim analysis of immunogenicity will be performed for all subjects through the Day 43 visit. Site staff and Sponsor personnel involved in study conduct will remain blinded to treatment assignments for this interim analysis. The final analysis will be performed when all data up to the study end (Day 387) are available. Analysis will be done on fully unblinded data set by the Sponsor and all data will be presented in the final study report.		
Data Monitoring Committee: No Data Monitoring Committee (DMC) is planned in		

Name of Sponsor: Seqirus, Inc.	Protocol number: V89_18	BB-IND No. 13,536
this study.		

Table 2: Times and Events Table, Scheduled Subject Contacts 1 – 17

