7.4.2.3 Sample Size and Power Considerations of Co-Primary Objectives

Data observed in previous studies in similar sets (V89_04 in subjects 18-64 years of age; V89_13 in subjects > 65 years of age) showed a variability of the post vaccination titers ranging from 0.75 to 0.88 (in the log scale). With the proposed sample size, assuming a standard deviation of 0.85 for the log₁₀ antibody titers (for each vaccine lot), approximate pairwise equivalence of factor 1 and independency, a single equivalence test based on 718 subjects per lot group has a power of 95%. The resulting overall power is approximately 86%, because the total number of comparisons is three. To account for dropouts (approximately 10%), a total of $n=798$ per lot should be recruited.

Data observed in previous studies in similar populations (V89_04 in subjects 18- <65 years of age; V89_13 in subjects > 65 years of age) showed a proportion of 86% of subjects aged 18 to <65 years and a proportion of 81% of subjects aged 65 years and older achieving an HI antibody titer of $\geq 1:40$. With a sample size of 1077 evaluable subjects from the pooled lots there is an overall power of approximately 98% to achieve the CBER criteria (HI antibody titer $\geq 1:40$ for at least 70% of the subjects aged 18 to <65 years, and for at least 60% of the subjects aged 65 years and older). To account for dropouts (approximately 10%), a minimum sample size of $n=1197$ for all lots combined are needed.

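### The power figures for the CBER co-primary (98%, 82% to >99%, >.999) disagree with each other and with the plan's inputs, and the power of the study-success rule, about 88%, is not stated

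*Protocol*

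**What the plan says.** Protocol 7.2.1 sets out two stages. Lot consistency requires that "the two-sided 95% confidence intervals (CIs) of all the three pairwise comparisons" of the lot GMTs "fall within 0.667 and 1.5". The lots are then pooled and the HI ≥1:40 criterion is assessed in each age cohort: the lower 95% confidence limit must reach 70% for ages 18 to <65 and 60% for ages ≥65. The synopsis gives the same order: "After demonstrating success of the lot-to-lot consistency, the achievement of the CBER criteria (co-primary objective) will be claimed if" the lower limit meets the threshold. The overall rule in 7.2.1 begins "The study will be considered a success if both lot-to-lot consistency for subjects aged" 18 and over, and adds the HI ≥1:40 criterion in both cohorts.

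Power for the CBER criteria is stated in several places:

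- Protocol 7.2.1: "The overall power to fulfill those CBER criteria is 98" percent.
- Protocol 7.4.2.3, and the text of both memos in SAP Appendix A: "there is an overall power of approximately 98% to achieve the CBER criteria".
- Protocol synopsis: 82% to >99%, depending on the cohort.
- SAP Appendix A, 20.1, nQuery table: 99% for each cohort at n = 1077.
- SAP Appendix A, 20.2, exact calculation: >.999 for each cohort at n = 1077.

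Power for lot consistency is given as 95% for one pair and about 86% for all three, in the synopsis, in 7.4.2.3 and in both memos. Section 7.2.1 does not repeat it.

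**The concern.** One quantity, the chance of meeting the CBER criteria, has values that cannot all be right. Joint power over two cohorts cannot exceed the smaller of the two cohort powers. If one cohort had 82%, the joint figure could not be 98%; if both exceed .999, the joint figure is above 99%, not 98%.

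The only power figure in the section that defines study success is also not the power of study success. That needs lot consistency as well, so its power cannot exceed that of the lot stage. A reader who wants the chance that the trial succeeds has to find the 86% elsewhere, see that it limits the rule, and know that the CBER stage adds almost no further risk. The stakes are the accuracy of the stated operating characteristics. Sample size and decision rules are not affected.

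**Working it through.** **Inputs.** Protocol 7.4.2.3 and SAP Appendix A: 718 evaluable per lot, "assuming a standard deviation of 0.85" on the log10 scale, true lot ratio 1, margin ±0.176, one-sided α 0.025 per limit. Earlier studies "showed a variability of the post vaccination titers ranging from 0.75 to 0.88 (in the log scale"). Assumed HI ≥1:40 rates: 86% (18 to <65) and 81% (≥65). The synopsis gives 1077 as the number per age cohort.

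**1. The printed 98%.** The nQuery table shows 99% twice, and 0.99 × 0.99 = 0.980. This matches, although the documents do not say it is how the figure was formed. The 99% is not an exact value. By the memo's normal-approximation method, the n that gives 99% power is

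n = [(1.96·√(p0(1−p0)) + 2.326·√(p1(1−p1))) / (p1−p0)]²,

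which is 114 for 70% against 86% and 80 for 60% against 81%, far below 1077.

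**2. CBER power from the inputs.** The lower limit of the exact two-sided 95% interval first reaches 70% at 784/1077 and 60% at 679/1077.

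| Cohort | Expected responders | Binomial SD | Distance above cut-off |
|---|---|---|---|
| 18 to <65 | 1077 × 0.86 = 926.2 | 11.39 | (926.2 − 784)/11.39 = 12.5 SD |
| ≥65 | 1077 × 0.81 = 872.4 | 12.87 | (872.4 − 679)/12.87 = 15.0 SD |

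Power exceeds 99.9% in each cohort and 99% jointly. The exact check in SAP 20.2 uses one-sided 0.05 (critical values 780 and 674, which reproduce). That is looser than the written criterion but makes no practical difference here.

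**3. The synopsis 82%.** Solving for the true rate that gives 82% power at these cut-offs yields about 74.0% against the 70% threshold or 64.3% against the 60% threshold. Neither is near 86% or 81%.

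**4. Lot stage.** The standard error of a pair difference is 0.85 × √(2/718) = 0.04486. Single-pair power is about 2Φ((0.176 − 1.96 × 0.04486)/0.04486) − 1 = 2Φ(1.963) − 1 = 95.0%, as printed. The printed 86% is 0.95³ = 0.857, which treats the three pairs as independent. They are not, because each lot enters two pairs. Simulating three lot means with pooled-variance intervals (4,000,000 runs) gives 87.8% for all three.

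**5. The whole rule.** Both stages were simulated on the same log-normal titers (20,000 trials, 359 per lot per cohort, age-adjusted lot contrasts). The CBER stage passed in 100.0% of trials, and the joint result was 87.5%, equal to the lot-stage result in that run. That agrees with 87.8% within simulation error (standard error √(0.878 × 0.122/20,000) = 0.2 points).

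| Assumption, 718 per lot | Power of study success |
|---|---|
| SD 0.75, equal lots | 96.5% |
| SD 0.85, equal lots | 87.8% |
| SD 0.88, equal lots | 84.0% |
| SD 0.85, one lot off by ratio 1.1 | about 73% |
| SD 0.85, lots evenly spread over ratio 1.1 | about 77% |

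The ratio of 1.1 is the alternative tabulated in both memos. The one-lot figure is 73.4% with log10(1.1) = 0.0414 and 73.7% with the rounded 0.041 in the nQuery table.

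**The case against.** The strongest defence is that the 98% is properly scoped. In 7.2.1 it comes straight after a sentence that starts from lot consistency having been achieved and names both age cohorts, and it refers back to those criteria. The plan uses the word overall in the same way for the lot objective, where it means across the three pairs. Read like this, 98% is the power for both cohorts together, given the first stage, and it slightly understates the true value.

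The limiting figure is also in print. About 86% for the lot stage stands just before the CBER figure in 7.4.2.3 and precedes it in the synopsis, and it lies on the cautious side of 87.8%. Giving power objective by objective is a coherent choice.

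Most of this stands. A reader might infer that 98% is offered as the chance of study success, and that success power is therefore overstated by 10 points (98 against 88) or 14 points (98 against 0.86 × 0.98 = 84%). The documents do not support that. The comparison sets a conditional power against a joint one, and no loss of power is concealed.

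The defence does not remove the disagreement among 98%, 82% and >.999, nor supply a power for the success rule. The synopsis may rest on other rates, since it cites previous studies only as examples and prints no rates, but then those rates need to be stated.

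**Conclusion.** The point holds as a correction of stated figures. On the plan's inputs, CBER power is above 99.9% in each cohort and above 99% jointly. The 98% is low because it multiplies whole-percent output, and the synopsis 82% cannot be obtained from rates of 86% and 81% with 1077 per cohort. The power of the success rule in 7.2.1 is about 88%, effectively all of it set by the lot stage, and it is not stated in either document.

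The 88% assumes SD 0.85, identical lots and 718 evaluable per lot. It ranges from 96.5% to 84.0% over the cited SDs of 0.75 to 0.88, and falls to about 73% if one lot differs by a ratio of 1.1. If baseline titer, age and center explain part of the variance in the planned ANCOVA, the effective SD would be smaller and the power higher; the documents give no figure for this. The design, margins, tests and sample size are not called into question.

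**What to change.** - **Protocol 7.2.1 and 7.4.2.3:** replace 98% with *>99% for both age cohorts together, given that lot consistency has been shown*.
- **Synopsis:** replace the range of 82% to >99% with *>99% in each cohort*, or state the true rates that give 82%.
- **Beside the success definition in 7.2.1:** add *Power to meet both lot consistency and the CBER criteria in both cohorts (study success) is approximately 88% at SD 0.85 with equal lot means, 84% at SD 0.88, and about 73% at SD 0.85 if one lot differs from the other two by a GMT ratio of 1.1.*
- **SAP section 5:** record the same correction there. Leave the memos of 17 June 2014 in Appendix A as they are, since they document what was calculated at the time.

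The cost is a wording amendment. The drawback is that the figure beside the success definition becomes less favourable.
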